10.2.3.5 Safety laboratory

Table LB 1 Safety laboratory measurements: Clinical chemistry (Full analysis set)

| Assessment (unit) | Result category | Assessment timepoint | IRL757 (N=6) | IRL757 (N=6) |
|-----------------------------------|-----------------|--------------------------|------------------|------------------|
| [PARAMETER 1] (unit) | Measured value | [Assessment timepoint 1] | | |
| | | n | xx | xx |
| | | Mean (SD) | x.xx (x.xx) | x.xx (x.xx) |
| | | Median (Min, Max) | x.xx (x.x, x.x) | x.xx (x.x, x.x) |
| | | 95% CI (lower, upper) | (x.xxxx, x.xxxx) | (x.xxxx, x.xxxx) |
| | | [Assessment timepoint 2] | | |
| | | n | xx | xx |
| | | Mean (SD) | x.xx (x.xx) | x.xx (x.xx) |
| | | Median (Min, Max) | x.xx (x.x, x.x) | x.xx (x.x, x.x) |
| | | 95% CI (lower, upper) | (x.xxxx, x.xxxx) | (x.xxxx, x.xxxx) |
| Change from baseline | | [Assessment timepoint 2] | | |
| | | n | xx | xx |
| | | Mean (SD) | x.xx (x.xx) | x.xx (x.xx) |
| | | Median (Min, Max) | x.xx (x.x, x.x) | x.xx (x.x, x.x) |
| | | 95% CI (lower, upper) | (x.xxxx, x.xxxx) | (x.xxxx, x.xxxx) |
| Relative change from baseline (%) | | [Assessment timepoint 2] | | |
| | | n | xx | xx |
| | | Mean (SD) | x.xx (x.xx) | x.xx (x.xx) |
| | | Median (Min, Max) | x.xx (x.x, x.x) | x.xx (x.x, x.x) |
| | | 95% CI (lower, upper) | (x.xxxx, x.xxxx) | (x.xxxx, x.xxxx) |

Data based on [population]. CI: Confidence interval. n: Number of observations. SD: Standard deviation. NC: Not calculated - number of evaluable observations less than 3. NA: Not available - no evaluable observations. SAS program: [PROGRAM NAME].sas.

Dataset version: ADXX YYYY-MM-DDTHH:MM:SS. Run by: [USERNAME] YYYY-MM-DDTHH:MM:SS. EDC data extracted: YYYY-MM-DDTHH:MM:SS.

Table LB 2 Safety laboratory interpretations: Clinical chemistry (Full analysis set)

| Assessment | Assessment timepoint | | IRL757 (N=6) | IRL757 (N=6) |
|---------------|--------------------------|------------|-----------------|-----------------|
| [PARAMETER 1] | [Assessment timepoint 1] | [RESULT 1] | xx/XX (xx%) | xx/XX (xx%) |
| | | [RESULT 2] | xx/XX (xx%) | xx/XX (xx%) |
| | | [RESULT 3] | xx/XX (xx%) | xx/XX (xx%) |
| | [Assessment timepoint 2] | [RESULT 1] | xx/XX (xx%) | xx/XX (xx%) |
| | | [RESULT 2] | xx/XX (xx%) | xx/XX (xx%) |
| | | [RESULT 3] | xx/XX (xx%) | xx/XX (xx%) |

Data based on [population]. SAS program: [PROGRAM NAME].sas.

Dataset version: ADXX YYYY-MM-DDTHH:MM:SS. Run by: [USERNAME] YYYY-MM-DDTHH:MM:SS. EDC data extracted: YYYY-MM-DDTHH:MM:SS.

Table LB 3 Safety laboratory measurements: Haematology (Full analysis set)

Same layout as Table LB 1

Table LB 4 Safety laboratory interpretations: Haematology (Full analysis set)

Same layout as Table LB 2

Table LB 5 Safety laboratory measurements: Coagulation (Full analysis set)

Same layout as Table LB 1

Table LB 6 Safety laboratory interpretations: Coagulation (Full analysis set)

[figure not shown]
Same layout as Table LB 2

10.3 Trial figures

10.3.1 Primary endpoints

10.3.1.1 Pharmacokinetic analysis

Figure PC 1 Geometric mean plasma concentrations of IRL757 over time 0-48h (lin-log) (Pharmacokinetic analysis set)

Example figure. Note that the numbers do not reflect real data. This template figure will be adjusted as needed depending on the collected data.

Data based on [population]. LLOQ is xx (unit). See listing 16.2.5-1 for a per subject LLOQ summary. lin: Linear. SAS program: [PROGRAM NAME].sas. Dataset version: ADXX YYYY-MM-DDTHH:MM:SS. Run by: [USERNAME] YYYY-MM-DDTHH:MM:SS. EDC data extracted: YYYY-MM-DDTHH:MM:SS.

Figure PC 2 Geometric mean plasma concentrations of IRL757 over time 0-48h (lin-lin) (Pharmacokinetic analysis set)

Same layout as Figure PC 1

Figure PC 3 Geometric mean plasma concentrations of 3 main metabolites of IRL757 over time 0-48h (lin-log) (Pharmacokinetic analysis set)

[figure not shown]
Same layout as Figure PC 1

Figure PC 4 Geometric mean plasma concentrations of 3 main metabolites of IRL757 over time 0-48h (lin-lin) (Pharmacokinetic analysis set)

Same layout as Figure PC 1

Figure PC 5 Individual plasma concentrations of IRL757 over time 0-48h by treatment (lin-log) (Full analysis set)

Individual values under LLOQ will be excluded from the figure. The full analysis set is used for individual graphs to ensure all data are plotted. However, ensure to clarify in a footnote if a subject is not in PKAS and why.

Example figure. Note that the numbers do not reflect real data. This template figure will be adjusted as needed depending on the collected data.

[figure not shown]
Data based on [population]. Individual values under LLOQ are excluded from the figure. LLOQ is xx (unit). See listing 16.2.5-1 for a per subject LLOQ summary. SAS program: [PROGRAM NAME].sas. Dataset version: ADXX YYYY-MM-DDTHH:MM:SS. Run by: [USERNAME] YYYY-MM-DDTHH:MM:SS. EDC data extracted: YYYY-MM-DDTHH:MM:SS.

Figure PC 6 Individual plasma concentrations of IRL757 over time 0-48h by treatment (lin-lin) (Full analysis set)

Same layout as Figure PC 5

10.3.1.2 Dose proportionality analysis

Figure PP 1 Dose proportionality for Cmax (Pharmacokinetic analysis set)

Example figure. Note that the numbers do not reflect real data.

Include a footnote with the regression equation. Include a footnote with the 90% CI for the slope parameter/coefficient in the model, the calculated acceptance region described in Section 9.1.1.1 and the conclusion of dose-proportionality/non-dose-proportionality. It will also be specified in the footnote which data are used.

Figure PP 2 Dose proportionality for AUC0-t (Pharmacokinetic analysis set)

Same layout as Figure PP 1

Figure PP 3 Dose proportionality for AUC0-inf (Pharmacokinetic analysis set)

Same layout as Figure PP 1

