- Vital signs (blood pressure, heart rate and body temperature)
- Safety laboratory measurements

Exploratory endpoints:

- Metabolite profile in plasma
- Profile of excreted metabolites in urine

Number of subjects planned

12 healthy subjects will be included in two dose groups.

Diagnosis and main eligibility criteria

Healthy elderly volunteers ≥ 65 and < 90 years of age, with a weight of 50 to 110 kg, who are willing to comply with trial procedures and who have given written consent, will be considered eligible for participation in the trial.

Methodology

Twelve (12) eligible and consenting subjects will be allocated to two dose groups. All subjects will be assigned to a single dose treatment with IRL757, 6 subjects to dose 1 and 6 subjects to dose 2.

Eligible subjects will be confined to the research clinic from the evening before first dosing (Day -1) until 48 hours following dosing. The subjects should be fasting overnight (10 hours) before dose administration on Day 1. A Follow-up Visit will be performed 5-10 days after administration of IMP.

Investigational Medicinal Products (IMP), dosage and mode of administration

IRL757 half-life is expected to be 4-10 hours.

IRL757 capsules**Duration of treatment**

Subjects included in the study will receive one dose of IRL757.

Duration of each subject's involvement in the trial

Subjects will be screened for eligibility according to trial-specific inclusion/exclusion criteria at Visit 1 (Screening visit) within 28 days prior to IMP administration.

A Follow-up Visit will be performed for all subjects 5-10 days after last administration of IMP.

Statistical methods

No formal sample size calculation has been performed for this trial. The size of the dose group is considered sufficient to provide adequate information on the safety and PK parameters for the purpose of this trial.

All statistical calculations will be performed using the SAS® version 9.4 or later (SAS Institute Inc., Cary, NC, USA). The statistical analyses will only include descriptive statistics reflecting the explorative nature of the trial. In general, the data will be presented by dose group.

Continuous data will be summarised by dose group using number of observations, mean, standard deviation (SD), median, minimum and maximum. Categorical data will be summarised by dose group using the number and percentage of subjects in each category.

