4.2 Trial objectives and endpoints

Table 1 Trial objectives and endpoints

| Objectives | Endpoints | Assessments | Analyses | Data display plan (DDP) |
|---|---|--|---|---|
| Primary objective | Primary endpoints | | | |
| To determine the single dose PK characteristics of IRL757 and its 3 main metabolites in elderly healthy volunteers. | 
IRL757 and 3 main metabolites: Area under the plasma concentration-time curve AUC_{0-t}, AUC_{0-24}, $AUC_{0-\infty}$, maximum concentration (C_{max}), time to maximum concentration (T_{max}), terminal elimination rate constant (λ_{z}), terminal half-life ($T_{1/2}$), amount excreted in urine (A_e)
 
IRL757 only: total apparent clearance of drug from plasma (CL/F), volume of distribution (V_z/F), fraction of the dose excreted in urine (F_e), renal clearance CL_R.
 | PK plasma and urine sampling | Descriptive statistics, Section 9.1.1 | Sections 10.2.2.1, 10.3.1.1 |
| | 
IRL757 and metabolites M5, M7: Dose proportionality after single oral doses based on AUC_{0-t}, $AUC_{0-\infty}$ and C_{max}
 | | Dose proportionality analysis, Section 9.1.1.1 | Section 10.3.1.2 |
| Secondary objective | Secondary endpoints | | | |
| To evaluate the safety and tolerability of IRL757 after single oral dosing in healthy elderly volunteers. | 
Frequency, seriousness and intensity of adverse events (AEs).
 
Physical examination
 
Electrocardiogram (ECG) recordings
 
Vital signs
 
Safety laboratory measurements
 
Columbia-Suicide Severity Rating Scale (C-SSRS)
 | 
AE reporting and questioning
 
Physical examinations
 
12-lead safety ECG
 
Blood pressure, heart rate, respiratory rate, body temperature
 
Blood sampling for haematology, clinical chemistry and coagulation
 
C-SSRS questionnaire
 | 
Descriptive statistics, Section 9.2.1
 
Descriptive statistics, Section 9.2.2
 
Descriptive statistics, Section 9.2.3
 
Descriptive statistics, Section 9.2.4
 
Descriptive statistics, Section 9.2.5
 
Listings, Section 9.2.6
 | 
Section 10.2.3.1
 
Section 10.2.3.2
 
Section 10.2.3.3
 
Section 10.2.3.4
 
Section 10.2.3.5
 
Section 10.4
 |
| Exploratory objective | Exploratory endpoints | | | |

| Objectives | Endpoints | Assessments | Analyses | Data display plan (DDP) |
|--|--|-----------------------------------|--|-------------------------|

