5.6 Significance level

All statistical hypotheses in this trial will be answered using two-sided 90% confidence intervals.

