9.1.1.1 Dose proportionality analysis

Dose-proportionality (an increase in dose corresponds to a proportional increase in PK outcome) after a single dose, will be assessed using the power model, i.e., linear regression modelling of AUC_{0-t} , AUC_{0-inf} , and C_{max} respectively on log-scale according to the formula:

$$\ln(PK) = \beta_0 + \beta_1 \times \ln(dose)$$

Let h be the highest dose and l be the lowest dose. Then the predicted PK geometric mean (back-transformed to normal scale) of the high dose is $e^{\beta_0}h^{\beta_1}$, and that of the low dose is $e^{\beta_0}l^{\beta_1}$. Let r be the maximal dose ratio, i.e., h/l . Dose proportionality corresponds to:

$$e^{\beta_0}h^{\beta_1}/e^{\beta_0}l^{\beta_1} = h/l \rightarrow (h/l)^{\beta_1-1} = r^{\beta_1-1} = 1$$

Let $\Theta_L=0.8$ and $\Theta_H=1.25$ be the lower and upper acceptance limits respectively, (0.8 and 1.25 being the industry standard limits). Dose-proportionality occurs when

$$\Theta_L < r^{\beta_1-1} < \Theta_H,$$

which on natural log scale equates to

$$\ln(\Theta_L) < (\beta_1 - 1)\ln(r) < \ln(\Theta_H) \rightarrow 1 + \frac{\ln(\Theta_L)}{\ln(r)} < \beta_1 < 1 + \frac{\ln(\Theta_H)}{\ln(r)}$$

Specifically, dose-proportionality is declared when the 90% CI for β_1 from the linear regression model on log scale lies entirely within the acceptance region:

$$\left[1 + \frac{\ln(0.8)}{\ln(r)}, 1 + \frac{\ln(1.25)}{\ln(r)}\right]$$

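### A missed dose-proportionality criterion would be printed as non-proportionality, even when the 90% CI contains a slope of 1

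*SAP*

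**What the plan says.** SAP Section 9.1.1.1 fits a power model to AUC0-t, AUC0-inf and Cmax and gives a rule that runs in one direction: "dose-proportionality is declared when the 90% CI for β_1 from the linear regression model on log scale lies entirely within the acceptance region". The region corresponds to 0.8 to 1.25 on the scale of r^(β1−1), where r is the ratio of high to low dose. The section does not say what follows when the interval crosses a limit.

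Section 5.6 adds that "All statistical hypotheses in this trial will be answered using two-sided 90% confidence intervals", again with nothing for an interval that straddles a limit. Section 5.1 only refers back to 9.1.1.1.

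The reporting instruction is in Section 10.3.1.2. The footnote to Figure PP 1 must give the regression equation, the 90% CI for the slope, and "the calculated acceptance region described in Section 9.1.1.1 and the conclusion of dose-proportionality/non-dose-proportionality". Figures PP 2 and PP 3 take the same layout. No section provides an inconclusive category.

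Table 1 in SAP Section 4.2 puts this analysis under the primary endpoints for IRL757, M5 and M7.

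**The concern.** The rule in Section 9.1.1.1 is an equivalence criterion. Meeting it supports proportionality within the limits. Missing it has two possible causes: exposure really departs from proportionality, or the interval is too wide to tell. The footnote's two labels do not separate these. A programmer who must print a conclusion, and who has a rule only for the positive one, will put every miss under *non-dose-proportionality*.

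That turns low precision into a stated departure from proportionality. With three analytes and three parameters in Table 1, up to 3 × 3 = 9 such conclusions could be printed for a listed primary endpoint. The design makes imprecision likely: two parallel groups of six, so between-subject variability drives the interval, and no sample size calculation.

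**Working it through.** The plan states no power or precision figure for this analysis, so there is none to reproduce. The question is how often the criterion is missed while the CI still contains a slope of 1.

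**Inputs from the documents.** Six subjects per dose group, two groups (SAP 4.3), hence 10 residual degrees of freedom; parallel groups (SAP 4.1); two-sided 90% CI (SAP 5.6); limits 0.8 and 1.25 (SAP 9.1.1.1).

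**Assumed.** Between-subject CV of 10% to 30% (the documents give none), log-normal data with equal variance in the two groups, all 12 subjects evaluable, and a true slope of exactly 1 unless stated.

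**Step 1: the redacted doses do not matter.** With two dose levels, (β1 − 1)·ln(r) is the difference between groups in mean log dose-normalised exposure. The CI for β1 and the acceptance region are both scaled by 1/ln(r), so r cancels. The resulting interval was checked against a regression fit for r = 2 and r = 4 and agreed.

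**Step 2: half-width against margin.** With s the pooled SD on the log scale:

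half-width = t(0.95, 10) × s × √(1/6 + 1/6) = 1.8125 × 0.5774 × s = 1.046 s

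The margin is ln(1.25) = 0.2231. Setting 1.046 s = 0.2231 gives s = 0.2132, and CV = √(exp(s²) − 1) = 21.6%. Above that observed CV the criterion cannot be met, even with a point estimate exactly on proportionality. For example, at an observed CV of 25%, s = √ln(1.0625) = 0.246 and the half-width is 0.258. A point estimate of exactly 1 then has a 90% CI of about 0.77 to 1.29. It is centred on proportionality but crosses both limits.

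**Step 3: how often.** Probabilities by numerical integration over the chi-square distribution of s² (10 df), confirmed by simulation:

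| Assumed CV | Criterion missed | Missed and CI contains slope 1 | Share of misses whose CI contains 1 |
|---|---|---|---|
| 10% | 5.1% | 2.5% | 49% |
| 15% | 44.1% | 35.4% | 80% |
| 20% | 79.7% | 69.8% | 88% |
| 30% | 98.3% | 88.3% | 90% |

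The third column reaches 50% at a CV of 16.8%.

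**Step 4: how often a definite negative would be supported.** Also under a true slope of 1, the CI lies wholly outside the region in under 0.1% of trials at CV 20% and 0.4% at CV 30%. The two-label footnote would print the negative in 80% and 98% of the same trials.

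**Step 5: if a positive non-proportional label is wanted.** The choice of boundary matters. With a true r^(β1−1) of 1.5:

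| Assumed CV | CI excludes slope 1 | CI wholly outside region | Difference (percentage points) |
|---|---|---|---|
| 15% | 99.7% | 62.8% | 37 |
| 20% | 95.0% | 43.7% | 51 |
| 30% | 72.0% | 26.1% | 46 |

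A CI can also exclude 1 and still lie inside the region. With a true slope of 1 and CV 10%, this happens in about 7% of trials.

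**The case against.** The SAP never says in words that a miss means non-proportional. Section 9.1.1.1 is silent on failure, so *not declared* is an equally literal reading, and the slash in a footnote template could be shorthand for *criterion not met*. The same footnote already prints the regression equation, the slope CI and the acceptance region, so a careful reader can see whether 1 is inside the interval. Geometric means and geometric CVs by dose group are reported separately. The trial is a 12-subject exploratory study, no visible section ties a decision to the label, and every percentage above depends on an assumed CV and an exactly proportional truth. The figure list does not name analytes, so even the count of nine is inferred from Table 1.

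Most of this stands as a limit on weight. The missing rule is certain; how a miss would be printed is inferred, though strongly, because a conclusion is required and only two are offered. The printed CI softens the problem but also means a footnote could carry a verdict that its own interval does not support. The exploratory character of the trial argues for the change: the protocol synopsis states that "The statistical analyses will only include descriptive statistics reflecting the explorative nature of the trial", which sits poorly with a definite negative drawn from a wide interval.

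**Conclusion.** The concern holds. The SAP leaves the outcome of a missed criterion undefined and then requires a conclusion from two labels, so an inconclusive result would most naturally be reported as a departure from proportionality. This textual finding does not depend on any assumed CV.

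Its practical size does. At a CV of 10% the problem is small; from about 17% upwards, a miss with slope 1 inside the CI is the majority outcome under exact proportionality. How often it would arise for IRL757, M5 or M7 cannot be judged from the documents. The effect is limited to the printed conclusion, since no estimate or interval changes. It should be fixed because it concerns a listed primary endpoint and the correction is nearly free.

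**What to change.** In SAP Section 9.1.1.1 add: *If the 90% CI for β1 does not lie entirely within the acceptance region, dose proportionality is not demonstrated; this alone is not evidence of non-proportionality.* In the footnotes to Figures PP 1–3 replace *non-dose-proportionality* with *dose proportionality not demonstrated*, next to the slope, CI and acceptance region already called for. Printing those quantities with no verdict would also do, and would fit the protocol's descriptive intent.

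If the sponsor wants a positive non-proportional label, its boundary should be fixed in advance: either the CI excludes 1, or the CI lies wholly outside the region. The choice is the sponsor's. If the first is chosen, the SAP must also say which label takes precedence when a CI excludes 1 but lies inside the region.

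The cost is one sentence and one footnote template. No data or subjects are added, and under the main fix no proportional verdict changes. The downside is that real departures are also labelled *not demonstrated* and have to be read from the CI.

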10.4 Trial listings

16.2.1 Discontinued subjects

- Listing 16.2.1- 1 Discontinued subjects
- Listing 16.2.1- 2 Non-eligible subjects
- Listing 16.2.1- 3 Disposition (All subjects)
- Listing 16.2.1- 4 Subject visits (All subjects)
- Listing 16.2.1- 5 Subject elements (All subjects)

16.2.2 Protocol deviations

- Listing 16.2.2- 1 Protocol deviations (All subjects)

16.2.3 Subjects excluded from the efficacy analysis

- Listing 16.2.3- 1 Population definitions (All subjects)

16.2.4 Demographic data

- Listing 16.2.4- 1 Demography (All subjects)
- Listing 16.2.4- 2 Medical History (All subjects)
- Listing 16.2.4- 3 Prior and concomitant medications (All subjects)
- Listing 16.2.4- 4 Baseline events (All subjects)

16.2.5 Compliance and/or Drug Concentration Data

- Listing 16.2.5- 1 Plasma concentration data (All subjects)
- Listing 16.2.5- 2 Urine concentration data (All subjects)
- Listing 16.2.5- 3 Pharmacokinetic parameters (All subjects)
- Listing 16.2.5- 4 IMP administration (All subjects)

16.2.6 Individual Efficacy Response Data

NA

16.2.7 Adverse event listings (each subject)

- Listing 16.2.7- 1 Adverse events (All subjects)
- Listing 16.2.7- 2 Serious adverse events (All subjects)

16.2.8 Listings of individual laboratory measurements subject

- Listing 16.2.8- 1 Safety laboratory measurements: Clinical chemistry (All subjects)
- Listing 16.2.8- 2 Safety laboratory measurements: Haematology (All subjects)
- Listing 16.2.8- 3 Safety laboratory measurements: Coagulation (All subjects)
- Listing 16.2.8- 4 Other laboratory measurements (All subjects)

Pregnancy test, Drug test, Alcohol screen

- Listing 16.2.8- 5 Virology (All subjects)

16.2.9 Listings of vital signs, ECG, physical examination data by subject

- Listing 16.2.9- 1 Vital signs (All subjects)
- Listing 16.2.9- 2 ECG (All subjects)
- Listing 16.2.9- 3 Physical examinations (All subjects)

16.2.10 Other data by subject

- Listing 16.2.10- 1 Columbia-Suicide Severity Rating Scale (All subjects)
